T2D	Type 2 diabetes
TSS	KCCQ total symptom score
WoC	Withdrawal of consent

AMENDMENT HISTORY

Date /Version	Brief description of change
1 Feb 2017 / Version 1.0	Version 1.0 signed
19 Feb 2019 /Version 2.0	
Secondary objective for KCCQ changed from clinical summary score to total symptom score, following protocol update (protocol version 2.0, 26 October 2017) [Section 1.1.2, 3.2.3, 4.2.4.2]
 
AEs leading to a risk for lower limb amputations added to safety objective, following protocol update [section 1.1.3, 3.3]
 
Echocardiography substudy added to exploratory objective, following protocol update [section 1.1.4]
 
Clarification of prohibited concomitant medication added [section 2.2, 4.2.2]
 
The analysis of the KCCQ endpoint changed to a composite rank-based method, following FDA feedback regarding the initially proposed mixed model repeated measures approach. [Section 3.2.3, 4.1.1, 4.2.4.2]
 
Adjudication requirement for potential events related to eGFR decline was removed, following protocol update [Section 3, 3.2.4, 4.2]
 
Event types that are being withheld from reporting to health authorities limited to HF events and death (Renal events will not be withheld). [Section 3.3]
 
Definition of baseline diabetic status for subgroup analysis added [Section 4.1]
 
eGFR will be calculated from central laboratory creatinine values, rather than using eGFR calculated by central laboratory. [Section 4.1]
 
Clarification that the significance level will be determined based on the exact actual proportion of primary endpoints included in the interim analysis [Section 4.2]
 
Updates to the list of subgroups [Section 4.2.3.1, Table 1]
 
 • Diuretics removed due to small group of patients not on diuretics. • History of hypertension replaced by etiology of HF (Ischemic vs Non-ischemic/unknown). • Clarification that atrial fibrillation group will include patients with atrial flutter and be based on enrolment ECG • Definition of T2D subgroup clarified 
In consideration of large variability associated with few events, it has been specified that HRs with confidence intervals will not be presented if less than 15 events in a subgroup [Section 4.2.3.1]
 
Specification that ‘on+off’ treatment will be considered the primary analysis approach for fractures and amputations [section 4.2.5]

Date /Version	Brief description of change
23 July 2019 / Version 3.0	Statement about urinalysis data removed. This was included by mistake in version 1.0. No central laboratory measurements are collected in this study [Section 4.2.5.5]
	Statement about presentation of potential events of Fournier’s gangrene added [Section 4.2.5.4]
	Clarification that presentation of DKA will primarily be based on adjudicated DKA
	Statement about a primary analysis censoring date to be applied after a decision to stop the trial after interim analysis added [Section 5]
	Details of statistical methods, assumptions and references for the joint frailty model of recurrent HF events and CV death added based on FDA request. Details about Ghosh and Lin plot added. [section 3.2.2 and 4.2.4.1]
	Removed reference to the R package Sanon (Kawaguchi et al 2011) for derivation of the adjusted win ratio as the Mann-Whitney odds estimate and removed the intermediate step to explicitly calculate the standard error of the Mann-Whitney odds. The same statistic will be derived using SAS as described in Koch et al 1998 (reference added) [section 4.2.4.2, Estimation of treatment effect]
	Additional details regarding responder analysis of KCCQ TSS added [section 4.2.4.2, Estimation of treatment effect].
	
 • Handling of patients whose baseline value is too high/low to make it possible to achieve the threshold for improvement/deterioration. • Details of logistic regression of the proportion of patients achieving the responder thresholds added. • Responder analysis by thresholds derived from anchor-based analysis added.
	Clarification added regarding the variable representing the number of HF events in multiple imputation of missing TSS values. [section 4.2.4.2, Handling of missing data]
	Clarification of use of imputed TSS values in responder analysis [section 4.2.4.2, Handling of missing data]
Correction: Descriptive statistics for KCCQ scores will be presented at 4 and 8 months [section 4.2.4.2, Supportive and sensitivity analyses]	
Correction to clarify how the sensitivity analysis of change from baseline TSS is different from the main analysis in terms of handling patients who died. [section 4.2.4.2, Supportive and sensitivity analyses]	
Correction: Removed creatinine clearance from laboratory variables to be summarized. Assessment of creatinine clearance is not defined in the study protocol. [section 4.2.5.5]	

Date /Version	Brief description of change
	
Marked lab abnormality criteria for creatinine clearance < 45 mL/min and eGFR < 45 mL/min/1.73m² were removed since not considered appropriate criteria for abnormality in the enrolled study population and had been included by mistake. [Appendix A].
 
The criterion serum creatinine $\geq 1.5 \times$baseline was retained and serum creatinine $\geq 2 \times$baseline was added.
 
Added Appendix B describing the estimation of clinically meaningful thresholds for KCCQ TSS.

1. STUDY DETAILS

1.1 Study objectives

1.1.1 Primary objective

Primary Objective:	Outcome Measure:
To determine whether dapagliflozin is superior to placebo, when added to standard of care, in reducing the incidence of CV death or a HF event (hospitalization for HF or equivalent HF event, ie an urgent HF visit).	Time to the first occurrence of any of the components of this composite: 
 1. CV death 2. Hospitalization for HF 3. An urgent HF visit

1.1.2 Secondary objectives

Secondary Objective:	Outcome Measure :
To compare the effect of dapagliflozin versus placebo on CV death or hospitalization for HF.	Time to the first occurrence of either of the components of this composite: 
 1. CV death 2. Hospitalization for HF
To compare the effect of dapagliflozin versus placebo on total number of recurrent HF hospitalizations and CV death.	Total number of (first and recurrent) HF hospitalizations and CV death.
To compare the effect of treatment with dapagliflozin versus placebo on the Kansas City Cardiomyopathy Questionnaire (KCCQ) total symptom score for HF symptoms.	Change from baseline measured at 8 months in the total symptom score of the KCCQ, a specific HF patient reported outcome questionnaire.

To determine if dapagliflozin compared with placebo reduces the incidence of a composite endpoint of worsening renal function.
	
Time to the first occurrence of any of the components of this composite:
 
 1. $\geq 50\%$ sustained decline in eGFR 2. Reaching End Stage Renal Disease (ESRD) 
 – Sustained eGFR <15 ml/min/1.73m² or, – Chronic dialysis treatment or, – Receiving a renal transplant 3. Renal death

To determine whether dapagliflozin, compared with placebo, reduces the incidence of all-cause mortality.
	
Time to death from any cause.

1.1.3 Safety objectives

Safety Objective:
	
Outcome Measure :

To evaluate the safety and tolerability of dapagliflozin in this patient population.
	
 1. Serious Adverse Events (SAEs) 2. Discontinuation of IP due to Adverse Events (DAEs) 3. Changes in clinical chemistry/haematology parameters 4. Adverse events of interest (volume depletion, renal events, major hypoglycaemic events, fractures, diabetic ketoacidosis (DKA), AEs leading to amputation and AEs leading to a risk for lower limb amputations [“preceding events”])

1.1.4 Explorative objectives

Exploratory Objective:	Outcome Measure :
To compare the effect of dapagliflozin versus placebo on an expanded composite outcome reflecting worsening of HF.	Time to the first occurrence of any of the components of the expanded composite worsening HF outcome: 4. CV death 5. Hospitalization for HF 6. An urgent HF visit 7. Documented evidence of worsening HF symptoms/signs leading to initiation of a new treatment for HF sustained for at least 4 weeks or augmentation of existing oral therapy for HF (eg, increase in dose of diuretic) sustained for at least 4 weeks.
To determine whether dapagliflozin compared with placebo will have effect on New York Heart Association (NYHA) class.	Change in NYHA class from baseline.
To determine whether dapagliflozin compared with placebo will reduce the incidence of diagnosis of AF in patients without history of AF at baseline.	Proportion of patients without history of AF at baseline with a new diagnosis of AF during the study.
To determine whether dapagliflozin compared with placebo will result in a reduction of the incidence of hyper – and hypokalaemia.	Time to the first occurrence of each of any of the following central lab levels of serum potassium: 
 • >6.0 mmol/L • >5.5 mmol/L • <3.5 mmol/L • <3.0 mmol/L
To determine whether dapagliflozin compared with placebo will affect the number of events of doubling of serum creatinine.	Number of events with doubling of serum creatinine (compared with the most recent laboratory measurement).
To determine whether dapagliflozin compared with placebo will reduce the incidence of diagnosis of T2D in patients without diabetes at baseline.	Proportion of patients without T2D at baseline with a new diagnosis of T2D during the study.
To determine whether dapagliflozin compared with placebo will have effect on HbA1c in T2D subgroup.	Changes in HbA1c from baseline.

To determine whether dapagliflozin compared with placebo will have an effect on systolic BP.	Change in systolic BP from baseline.
To determine whether dapagliflozin compared with placebo will have an effect on body weight.	Change in body weight from baseline.
To determine whether dapagliflozin compared with placebo will reduce the incidence of myocardial infarction (MI).	Time to first fatal or non-fatal MI.
To determine whether dapagliflozin compared with placebo will reduce the incidence of any stroke (ischemic, hemorrhagic, or undetermined).	Time to first fatal or non-fatal stroke of any cause.
To compare the effect of dapagliflozin versus placebo on health status assessed by Patient Global Impression of Change (PGIC) and Patient global impression of severity (PGIS) questionnaires.	Changes in health status measured by PGIC and PGIS.
To compare the effect of dapagliflozin versus placebo on health status assessed by EuroQol five-dimensional five-level questionnaire (EQ-5D-5L) to support health economic analysis and health technology assessment.	Changes in health status measured by EQ-5D-5L.
To collect and analyse pharmacokinetic (PK) samples for dapagliflozin concentration.	Not applicable. Results will be reported separately.
To assess cardiac structure and function with echocardiography at baseline and 8 months follow-up.	Not applicable. Results will be reported separately.
To collect and store samples of plasma and serum for future exploratory biomarker research.	Not applicable. Results will be reported separately.

1.2 Definitions

1.2.1 Primary analysis censoring date

The executive committee and AstraZeneca will monitor the accrual of endpoint events and when appropriate define the primary analysis censoring date (PACD) at which time at least the pre-defined target number of 844 events for the primary composite endpoint is expected to have occurred. The study sites will be instructed to plan for study closure visits to be performed after PACD.

The analyses of the endpoint events will include events with onset on or prior to PACD. Event free patients who have not been prematurely censored due to incomplete information (see

Section 3.1 and 3.2) will be censored at PACD. Endpoint events with onset after PACD will also be adjudicated.

1.2.2 Withdrawal of informed consent

Withdrawal of consent (WoC) means withdrawal from study and should only occur if the patient does not agree to any kind of further assessment at all. No data after date of WoC should be collected, with the exception of vital status (dead or alive) at the end of the study collected from public sources, which will be included in the analysis of death from any cause as a sole outcome and in patient disposition summaries. Data collected on or prior to date of WoC will be included in analyses.

1.2.3 Discontinuation from study drug

Discontinuation from study drug does not mean WoC. Optimally, patients who discontinue from study drug should continue study visits according to plan until study closure. Alternatively, if the patient does not agree to this approach, modified follow-up should be arranged. Data from patients who did not withdraw consent will be included in the intention to treat (ITT) analyses irrespective of whether the event occurred before or following discontinuation of study drug.

1.2.4 Vital status

Known vital status at the end of the study will be defined when the patient is dead or has date last known alive on or after the PACD.

For patients who have withdrawn consent, the investigator will attempt to collect vital status from publicly available sources at study closure in compliance with local privacy laws/practices.

1.2.5 Lost to follow-up

The term lost to follow-up (LTFU) will be limited to patients with unknown vital status at the end of the study as defined in Section 1.2.4. Other measures will be used to describe incomplete follow-up of the primary endpoint (Section 4.1.5)

1.3 Study design

[figure not shown]
This is an international, multicentre, parallel group, event-driven, randomized, double-blind, placebo-controlled study in patients with chronic heart failure with reduced ejection fraction (HFrEF), evaluating the effect of dapagliflozin 10 mg versus placebo, given once daily in addition to background regional standard of care therapy, for the prevention of cardiovascular (CV) death or reduction of heart failure (HF) events.

It is estimated that approximately 7000 patients at approximately 500-600 sites in 20-25 countries will be enrolled to reach the target of approximately 4500 randomized patients. The investigational product (IP) will be added to the prescribed background therapy for HF (and

background therapy for T2D when applicable) as considered appropriate by the investigator and in accordance with regional standards of care.

The anticipated duration of the study is approximately 33 months. The study closure procedures will be initiated when the predetermined number of adjudicated primary endpoints is predicted to have occurred (844). This date, which in the clinical study protocol (CSP) is termed study end date (SED) will be the common censoring date for efficacy time-to-event analyses. Thus, it will in this SAP be termed the primary analysis censoring date (PACD, Figure 1).

Figure 1 Study flow chart

1.3.1 Randomization

Patients will be randomized 1:1 to either dapagliflozin 10 mg or placebo. Randomization will be stratified by type 2 diabetes (T2D) status at randomization (2 levels: with T2D; without T2D). T2D for stratified randomization is defined as established diagnosis of T2D or HbA1c more or equal to 6.5% (48 mmol/mol) shown at central laboratory test at enrolment (visit 1). See section 4.1 for definition of baseline diabetic status for analysis.

Randomization will be performed in balanced blocks of fixed size. The randomization codes will be computer generated and loaded into the IxRS (Interactive Voice/Web Response System) database.

The number of randomized patients with and without T2D will be monitored in order to ensure a minimum of 30% in each sub-population. Randomization may be capped (ie, no more patients can be randomized in a specific sub-population) if the pre-determined limit is reached.

Randomization of patients based on geographic region will be monitored to ensure global representation. LVEF category, NYHA class and atrial fibrillation status may be capped in IxRS to avoid over- or under-representation of these patient subgroups.

1.4 Number of patients

The primary objective of the study is to determine the superiority of dapagliflozin versus placebo in reducing the incidence of the primary composite endpoint. Assuming a true hazard ratio (HR) of 0.80 between dapagliflozin and placebo, using a one-sided alpha of 2.5%, 844 primary endpoint events will provide a statistical power of 90% for the test of the primary composite endpoint. This is based on an overall 1:1 allocation between dapagliflozin and placebo. The study is event-driven. The assumed HR of 0.80 is considered as clinically relevant and has taken into account the HF outcomes in the EMPA-REG trial (Fitchett et al 2016).

With an annual event rate of 11% in the placebo treatment group, 4500 patients are estimated to provide the required number of primary events, based on an anticipated recruitment period of 18 months and an average follow-up period of approximately 24 months. The assumed placebo event rate of 11% is based on a review of recently published clinical studies in the HFrEF population, including the PARADIGM-HF trial (McMurray et al 2014). The number of patients with incomplete follow-up of endpoints is expected to be small; hence, these are not considered in the determination of the sample size.

This study is a group sequential design study with one interim analysis at 75% of the adjudicated target number of events using Haybittle-Peto boundary (a one-sided alpha=0.001), leaving a one-sided alpha of 2.496% for the final analysis.

2. ANALYSIS SETS

2.1 Definition of analysis sets

2.1.1 Full analysis set

All patients who have been randomized to study treatment will be included in the full analysis set (FAS) irrespective of their protocol adherence and continued participation in the study. Patients will be analysed according to their randomized IP assignment, irrespective of the treatment actually received. The FAS will be considered the primary analysis set for the primary and secondary variables and for the exploratory efficacy variables.

2.1.2 Safety analysis set

All randomized patients who received at least 1 dose of randomized treatment will be included in the safety population. Patients will be analysed according to the treatment actually received. For any patients given incorrect treatment, ie randomized to one of the treatment groups but actually given the other treatment, the treatment group will be allocated as follows: Patients who got both incorrect and correct treatment will be analyzed according to their

randomized treatment. Patients who got only the incorrect treatment will be analyzed according to that treatment.

The safety analysis set will be considered the primary analysis set for all safety variables.

2.2 Violations and deviations

The important protocol deviations listed below will be summarised by randomized treatment group

- Patients who were randomised but did not meet inclusion and exclusion criteria
- Patients who received the wrong study treatment at any time during the study.
- Patients who received prohibited concomitant medication, which for this study is limited to open label SGLT2 inhibitors taken in combination with IP.

As the primary analysis is intention-to-treat analysis, protocol deviation will not imply exclusion from the primary analysis.

3. PRIMARY AND SECONDARY VARIABLES

Potential endpoint events and event dates will be adjudicated by an independent clinical event adjudication (CEA) committee. The committee members will not have access to the treatment codes for any patient. The CEA procedures and event definitions will be described in the CEA charter.

The primary and secondary efficacy variables and their components will only include HF events confirmed by the CEA. Deaths adjudicated as ‘cause undetermined’ with regard to CV death or non-CV death will be included as CV death in the primary efficacy analyses.

All adjudicated events from randomization until WoC or PACD will be included in the analysis of primary and secondary endpoints, except for the analysis of all-cause death as a sole outcome, which also will include deaths (not adjudicated) after WoC, but on or before PACD.

For analysis of time to first event, data will be expressed as two variables:

- A binary variable indicating whether the event in question occurred, or the patient was censored.
- An integer variable for the number of days from randomization to the first occurrence of an event (start date of the event – randomization date + 1), or for event free patients, from randomization to censoring (censoring date – randomization date + 1).

Event free patients will be censored as described below for each respective endpoint.

3.1 Primary variable

The primary efficacy variable is time from randomization to the first occurrence of any event in the composite of CV Death, hospitalization for HF or an urgent HF visit.

The three components of the endpoint will be individually adjudicated by the CEA committee.

Patients who did not have an endpoint event will be censored at the earliest of date of WoC or non-CV death when applicable, and otherwise at the earliest of date of last clinical event assessment or PACD. Last clinical event assessment is defined as the last date when the event assessment question for a potential heart failure event was completed on the eCRF event assessment page. It is expected that patients alive and under study follow-up will have a clinical event assessment at their SCV after PACD

In analysis of hospitalization for HF and urgent HF visit to examine the contribution of each component of the composite endpoint, date of death from any cause will be an additional point of censoring.

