3.2.5 Death from any cause

The efficacy variable is time to from randomization to death from any cause. All deaths on or prior to PACD, including death after WoC will be included. Patients who are alive will be censored at the earliest of date last known alive and PACD.

Deaths occurring after WoC will not be adjudicated. For such events, the date of death will be collected only in eCRF.

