4.1.5 Vital status and follow-up of endpoints

Potential endpoints will be collected and adjudicated from randomization throughout the study until and including the patient's last visit. The investigator will attempt to collect vital status (dead or alive) at the end of the study for all patients, including vital status from publicly

available sources for patients who have withdrawn consent, in compliance with local privacy laws/practices.

Known vital status at the end of the study will be defined when the patient is dead or has date last know alive (derived from the eCRF final status form) on or after the PACD. In patient disposition the number of patients who are dead, alive or with unknown vital status will be reported separately for patients who did/did not withdraw consent. The term lost to follow-up (LTFU) will be limited to only patients with unknown vital status.

Follow-up of the primary endpoint will be defined in terms of completion of the event assessment question for a potential HF event as described for censoring in Section 3.1. Thus a patient that is not LTFU, ie with known vital status, may have incomplete follow-up of endpoints.

Complete follow up of the primary endpoint will be defined as the patient had a primary endpoint event, died from non-CV death or had complete event assessment on or after the PACD.

In addition to the number and percent of patients with complete follow-up, the proportion of total patient time with complete follow-up will be reported per treatment group.

Patient time with complete follow-up will be defined as time from randomization until the earliest of first primary endpoint event, death, WoC, censoring due to incomplete event assessment (in cases where last complete event assessment is prior to PACD) or PACD. The denominator, representing maximum complete follow-up, will be the time to first primary endpoint event, death or PACD.

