4.2.3 Analysis of the primary efficacy variable

The primary variable is the time to first event included in the primary composite endpoint. The primary analysis will be based on the ITT principle using the FAS, including events with onset on or prior to PACD, adjudicated and confirmed by the CEA committee.

In the analysis of the primary composite endpoint, treatments (dapagliflozin versus placebo) will be compared using a Cox proportional hazards model with a factor for treatment group, stratified by T2D status at randomization, and adjusting for history of hospitalization for heart failure. The analysis will use WoC, non-CV death, last clinical event assessment and PACD for censoring of patients without any primary event as described in Section 3.1. The Efron method for ties and p-value based on the score statistic will be used. The event rates, p-value, HR, and 95% confidence interval will be reported.

The contribution of each component of the primary composite endpoint to the overall treatment effect will be examined. In the analysis of the components, all first event of the given type will be included irrespective of any preceding non-fatal composite event of a different type. Consequently, the sum of the number of patients with events in the component analysis will be larger than the number of patients with composite events. Methods similar to those described for the primary analysis will be used to separately analyze the time from randomization to the first occurrence of each component of the primary composite endpoint.

Kaplan-Meier estimates of the cumulative proportion of patients with event will be calculated and plotted, for the composite endpoint and for the individual components.

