5. INTERIM ANALYSES

An interim analysis is planned to be performed when approximately 75% of the primary events have been adjudicated, using a Haybittle-Peto rule. There will in principle be one planned interim analysis, with the possibility for the DMC to do subsequent interim analysis if

they deem necessary. The significance level for the final analysis will be determined by the Haybittle-Peto function based on the actual number and timing of interim analyses.

The interim analysis will assess superiority of dapagliflozin to placebo. The interim analysis will use a one-sided alpha level of 0.001. At the interim analysis, the primary composite endpoint will be first tested at the specified alpha level. If superiority is achieved for the primary endpoint, then the superiority of dapagliflozin to placebo on CV death will be tested at a one-sided alpha level of 0.001. If CV death is significant, then an action is triggered whereby the DMC will evaluate the totality of the available efficacy data and safety data, to determine if benefit is unequivocal and overwhelming such that the DMC recommends ending the study.

If the interim analysis leads to a decision to terminate the study early based on the pre-defined stopping guidelines for superiority, the executive committee will define a PACD, on or after which study closure visits will commence. The study report will be based on all events occurring on prior to the PACD.

If the study is stopped for superiority at an interim analysis, then testing of secondary endpoints will continue down the hierarchy at a one-sided alpha level 0.001.

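### CV death has no censoring rule of its own: under Section 3.1 survivors can be censored at their last HF assessment while later CV deaths still count

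*SAP*

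**What the plan says.** - **Events counted (SAP Section 3).** "All adjudicated events from randomization until WoC or PACD will be included in the analysis of primary and secondary endpoints". There is no cut at the last assessment.
- **Censoring (Section 3.1).** Patients without a primary event who withdraw consent or die of non-CV causes are cut at that date. For all others the rule reads "otherwise at the earliest of date of last clinical event assessment or PACD". The assessment in question is dated by "the last date when the event assessment question for a potential heart failure event was completed on the eCRF event assessment page". It does not refer to vital status.
- **Components (Section 4.2.3).** "Methods similar to those described for the primary analysis will be used to separately analyze the time from randomization to the first occurrence". Section 3.1 adds a component-specific censoring point (death from any cause) for HF hospitalization and urgent HF visit. It adds nothing for CV death.
- **All-cause death (Section 3.2.5).** "Patients who are alive will be censored at the earliest of date last known alive and PACD".
- **Who can be affected (Section 4.1.5).** "Thus a patient that is not LTFU, ie with known vital status, may have incomplete follow-up of endpoints".
- **Use of CV death.** At the interim, if the primary endpoint crosses its boundary, "then the superiority of dapagliflozin to placebo on CV death will be tested at a one-sided alpha level of 0.001" (Section 5). CV death also has its own subgroup analyses (Section 4.2.3.1).

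**The concern.** Take a patient who has not withdrawn consent and whose HF assessments stop at month 6. If known to be alive at PACD, the patient is censored at month 6 in the CV-death analysis. If the same patient dies of CV causes at month 20, before PACD, the death counts, with 20 months of follow-up. Whether months 6 to 20 enter the risk set depends on the outcome. This goes beyond the usual assumption of non-informative censoring, because the rule itself creates the dependence.

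For the HF components, the last HF assessment is a sensible limit on what is known. For death it is not: vital status is collected separately, and the SAP already uses it for all-cause death. The same survivor can therefore have two different follow-up times in two mortality analyses of one trial.

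At stake are the reported CV-death rates, the CV-death hazard ratio overall and by subgroup, and the second of the two tests that lead to a possible early stop.

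**Working it through.** **The plan's own figures.** Schoenfeld's formula at HR 0.80, one-sided 2.5%, 90% power and 1:1 allocation gives 4 × (1.960 + 1.2816)² / (ln 0.80)² = 42.03 / 0.04979 ≈ 844 (845 rounded up). Power at 844 events is 90.0%. The Haybittle-Peto final level, with 0.001 spent at 75% information, is 0.02496. All agree with Section 1.4, and none depends on the point below.

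**Inputs.** From the SAP: 4500 patients, 1:1, 18 months of recruitment in a 33-month study, hence 15 to 33 months of follow-up. Assumed, because the SAP gives no figure: CV death at 5 to 8 per 100 patient-years; a fraction f of patients with incomplete HF assessment; the time of stopping uniform over each such patient's follow-up.

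**Rate inflation.** An affected survivor loses half of the follow-up on average, while no death is lost. Ignoring that those who die keep their time, the rate is multiplied by about 1 / (1 − 0.5f). The simulated ratio compares the placebo rate under the SAP rule with the rate under vital-status follow-up to PACD.

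| f | 1 / (1 − 0.5f) | Simulated, 5 per 100 PY | Simulated, 8 per 100 PY |
|---|---|---|---|
| 2% | 1.010 | 5.05/5.01 = 1.008 | 8.05/7.98 = 1.009 |
| 5% | 1.026 | 5.10/4.98 = 1.024 | 8.19/8.00 = 1.024 |
| 10% | 1.053 | 5.23/4.98 = 1.050 | 8.36/7.97 = 1.049 |

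This is about 0.5% per 1% incomplete.

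**Hazard ratio.** With fractions f1 (dapagliflozin) and f0 (placebo), the HR is multiplied by about (1 − 0.5·f0) / (1 − 0.5·f1). The simulated factor is the Cox HR under the SAP rule divided by the HR under vital-status follow-up, with a true HR of 1.

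| f1 v f0 | Formula | Simulated, 5 per 100 PY | Simulated, 8 per 100 PY |
|---|---|---|---|
| equal (2%, 5% or 10%) | 1 | 1.00 | 1.00 |
| 1% v 3% | 0.985/0.995 = 0.990 | 0.993/1.003 = 0.990 | 0.993/1.003 = 0.990 |
| 2% v 5% | 0.975/0.990 = 0.985 | 0.986/1.001 = 0.985 | 0.986/1.000 = 0.986 |
| 5% v 10% | 0.950/0.975 = 0.974 | 0.982/1.007 = 0.975 | 0.973/0.997 = 0.976 |
| 5% v 2% | 0.990/0.975 = 1.015 | 1.020/1.005 = 1.015 | 1.013/0.999 = 1.014 |

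For example, with an assumed true HR of 0.82 and 2% v 4% incomplete, 0.820 × 0.980/0.990 = 0.812. Reversed, it becomes 0.828.

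**Effect on a nominal test of CV death** (n = 4500, 6.5 per 100 PY, true HR 1, one-sided critical value 1.96, 4000 trials, Monte Carlo standard error about 0.25 points):

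- 2% v 5%: rejection in favour of dapagliflozin 3.6% under the SAP rule, against 2.1% with vital-status follow-up and 2.3% when deaths and survivors are both cut at the last assessment.
- 5% v 10%: 4.8%, against 2.6% under either symmetric rule.
- Equal fractions: no difference from the symmetric rules beyond simulation error.

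A hand check agrees. Deaths ≈ 4500 × (1 − e^(−0.13)) ≈ 549, so SE(log HR) ≈ 2/√549 = 0.085. The shifts ln 0.985 and ln 0.974 move z by about 0.18 and 0.30, giving Φ(−1.78) ≈ 3.7% and Φ(−1.66) ≈ 4.9%.

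None of this was computed at interim follow-up or at the 0.001 level.

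**The case against.** The strongest reply is that few patients are reached. A survivor is cut early only if the last HF assessment precedes PACD. Section 3.1 expects patients under follow-up to be assessed at the closure visit after PACD, and Sections 1.4 and 4.2.3.2 expect incomplete follow-up to be small. Patients who withdraw consent are treated symmetrically, since events and censoring both stop at WoC. The trial is double-blind, so a large imbalance in missed assessments is not the natural expectation. The interim test of CV death follows a primary result already past 0.001 and leads to a DMC review of all the data, not to an automatic stop. All of this stands and limits the size of the point.

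Two replies carry less weight. Section 4.2.3 says only that similar methods will be used, so carrying the rule over to CV death is an inference; but no other rule is given. Section 4.2.3.2 foresees sensitivity analyses for premature censoring, but for the primary endpoint and with content still to be decided, so it does not remove the asymmetry.

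A reader might also infer that Section 3.1 lets follow-up run past PACD, because its wording applies PACD only to patients without WoC or non-CV death. The rest of the SAP does not support that reading. Sections 1.2.1 and 1.3 make PACD the common censoring date, and Section 3 counts no later events. Even taken literally, with an assumed 3700 patients at risk, a closure window of 1 to 3 months and 1% to 3% per year with WoC or non-CV death, it adds at most 3700 × 0.03 × 3/12 ≈ 28 patients and 28 × 3/24 ≈ 3.5 patient-years, out of about 8100 (4500 × 2 × 0.9).

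Nor does Section 4.1.5 set up a rival rule. It treats non-CV death as complete follow-up, which agrees with censoring at that death.

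**Conclusion.** The point holds for CV death analysed alone, as a modest and conditional one. As written, the SAP counts CV deaths after the last HF assessment and drops the matching time of survivors. CV-death rates are then overstated by about 0.5% per 1% of patients with incomplete assessment. The hazard ratio is biased only if incompleteness differs between arms: by about 1% to 2.5% under the imbalances tried, in either direction. These sizes rest on the assumed death rate, fractions incomplete and uniform stopping time.

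A reader might infer that the trial's type I error is compromised. It is not shown to be. CV death alone is not in the final hierarchy of Sections 3.2 and 4.1.3, so the 3.6% and 4.8% above concern a nominal test under assumed imbalance. The change is still worth making, because the amount and balance of missing assessments were not known when the rule was set and the better date is already needed for all-cause death.

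**What to change.** Add one sentence to Section 3.1 and refer to it from Sections 4.2.3, 4.2.3.1 and 5: in every analysis of CV death alone, including the interim test and the subgroups, patients without a CV death are censored at the earliest of WoC, non-CV death, date last known alive (for patients not known to have died) and PACD.

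For the composites, add only that no censoring date may fall after PACD. Do not move non-CV deaths back to the preceding clinical event assessment: that would discard time that Section 4.1.5 regards as complete, while CV deaths between visits would still count at their own dates.

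The cost is two sentences and the reuse of a date already derived for Section 3.2.5. The 844 events, 90% power and 2.496% final level are unchanged.
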